- Stroke: A stroke is an interruption of the blood supply to any part of the brain. Rapid onset of a focal or global neurological deficit with at least one of the following: change in level of consciousness, hemiplegia, hemiparesis, numbness or sensory loss affecting one side of the body, dysphasia or aphasia, hemianopia, amaurosis fugax, or other neurological signs or symptoms consistent with stroke.

Duration of a focal or global neurological deficit  $\geq 24$  h; OR  $< 24$  h if therapeutic intervention(s) were performed (e.g., thrombolytic therapy or intracranial angioplasty); OR available neuroimaging documents a new hemorrhage or infarct; OR the neurological deficit results in death AND no other readily identifiable non-stroke cause for the clinical presentation (e.g., brain tumor, trauma, infection, hypoglycemia, peripheral lesion, pharmacological influences).

Diagnosis should be confirmed by a neurology or neurosurgical specialist utilizing a neuroimaging procedure (MR or CT scan or cerebral angiography) or lumbar puncture (i.e., spinal fluid analysis diagnostic of intracranial hemorrhage).

Documentation of a stroke or CVA consisting of acute loss of neurological function caused by an ischemic event with residual symptoms at least 24 hours after onset confirmed by CT or MRI scan or cerebral angiography of acute neurological event.

- Transient Ischemic attacks (TIA): A transient ischemic attack is a "mini-stroke" caused by temporary disturbance of blood supply to an area of the brain, which results in a sudden, brief decrease in brain function. Clinical symptoms similar to stroke but last for less than 24 hours.

Documentation of TIA neuroimaging without tissue injury consistent with acute loss of neurological function caused by an ischemic event with resolution of symptoms within 24 hours after onset.

- Atrioesophageal fistula: An atrioesophageal fistula is defined as a connection between the atrium and the lumen of the esophagus.

Documentation of an atrial-esophageal fistula: A CT or MRI scan and documentation of esophageal erosion combined with evidence of a fistulous connection to the atrium such as air emboli, an embolic event, or direct observation at the time of surgical repair.

- Phrenic Nerve Injury: Injury to the phrenic nerve that may be caused during the surgical procedure to access the heart or during ablation (epicardial or endocardial).

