10.1 Major Adverse Events (MAEs)

MAEs (listed below and defined in Section 1.5.3 of the study protocol) will be adjudicated by the CEC. These adjudicated events will be recorded in a spreadsheet following the committee meeting and provided to the sponsor or designee after each meeting. The complete list of adjudicated events will be finalized prior to database lock and incorporated into an analysis dataset, separate from the adverse event dataset. MAEs will be summarized by event type and treatment arm, based on onset date:

- Date of study procedure through the 30th day post-procedure
- 31st day post-procedure through 12 months (365th day) post-procedure
- Overall

The MAEs for this study are as follows:

- Cardiac tamponade/perforation

- Severe pulmonary vein stenosis
- Excessive bleeding
- Myocardial infarction
- Stroke
- Transient ischemic attack
- Atrioesophageal fistula
- Phrenic nerve injury
- Death

The primary safety analysis will be to document an acceptable risk profile. This criterion will be defined as an acceptable level of MAEs. It is estimated that the true incidence rate for MAEs in this study population is no more than 12%. A 95% one-sided confidence interval for the investigational treatment arm based on a 102 subject sample size is 5%, resulting in an upper bound of MAEs being less than 20%. This result would document an acceptable risk profile for the investigational arm.

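### Protocol 1.5.3 gives two conflicting rules for stroke, and neither the protocol nor the SAP says which one governs adjudication of this primary safety component

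*Protocol*

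**What the plan says.** Stroke and TIA are both MAE components of the primary safety endpoint (protocol 1.5.3), which covers the procedure to 30 days in the convergent arm.

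The stroke item first gives a definition with alternative routes. A focal or global deficit of at least 24 h qualifies. A shorter one qualifies "if therapeutic intervention(s) were performed (e.g., thrombolytic therapy or intracranial angioplasty"). Imaging alone can qualify an event: "OR available neuroimaging documents a new hemorrhage or infarct". So can a fatal outcome: "OR the neurological deficit results in death AND no other readily identifiable non-stroke cause for the clinical presentation". The next paragraph, on confirming the diagnosis, accepts neuroimaging or "lumbar puncture (i.e., spinal fluid analysis diagnostic of intracranial hemorrhage").

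The item then closes with a documentation sentence that requires a sudden deficit "caused by an ischemic event with residual symptoms at least 24 hours after onset confirmed by CT or MRI scan or cerebral angiography".

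The TIA item describes the event in one line, "Clinical symptoms similar to stroke but last for less than 24 hours", and has its own documentation sentence. That sentence begins "Documentation of TIA neuroimaging without tissue injury" and also requires an ischemic cause and resolution within 24 h.

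The SAP adds no stroke rule of its own. Section 10.1 says "MAEs (listed below and defined in Section 1.5.3 of the study protocol) will be adjudicated by the CEC". Protocol 8.1 lists stroke and TIA by name only.

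**The concern.** The documentation sentence drops three things that the definition includes: hemorrhage, every route for a deficit under 24 h, and confirmation by lumbar puncture. An event can therefore be a stroke by the definition and fail the sentence that says how a stroke is documented. The TIA documentation does not catch all of these events, because it excludes non-ischemic causes and any tissue injury.

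Two things are at stake. First, adjudication by the CEC is meant to keep the primary safety endpoint objective, and an endpoint with two rules depends on which one a committee member reads. Second, the convergent arm's MAE rate is judged against an upper bound of 20% (protocol 9.7, SAP 10.1), and events that drop out lower that rate.

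Hemorrhage is a foreseeable event type here. Attachment E calls for an ACT of 300 to 400 seconds during catheter ablation and systemic anticoagulation for at least two months afterwards, which spans the 30-day window. Stroke is also one of four event types with expedited reporting to FDA (protocol 1.3 and 8.5); TIA is not. Recording a stroke as a TIA could therefore affect reporting as well as the count.

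**Working it through.** **Step 1. The rules side by side.** Suppose the two documentation sentences decide whether an event qualifies.

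| Event | Stroke definition | Stroke documentation | TIA documentation | Result |
|---|---|---|---|---|
| Ischemic deficit, 24 h or longer, confirmed on CT, MRI or angiography | met | met | fails (duration) | stroke |
| Non-fatal hemorrhagic stroke | met | fails (not ischemic) | fails (not ischemic) | neither |
| Deficit under 24 h with new infarct, treated or not | met | fails (no symptoms at 24 h) | fails (tissue injury) | neither |
| Deficit under 24 h, treated, no infarct | met | fails (no symptoms at 24 h) | can be met | TIA, still an MAE |
| Fatal stroke | met | may fail | not needed | counted as Death |

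Two kinds of non-fatal event can leave the count, and a third can change category. Treated and untreated short deficits with infarct fail for the same reason, so they are one case. A hemorrhage confirmed only by lumbar puncture fails the stroke sentence twice, on cause and on method. The excessive bleeding component is not a dependable substitute for intracranial hemorrhage: it needs a device- or procedure-related injury plus transfusion or a hematocrit fall of at least 20%.

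**Step 2. Are documentation lines criteria?** Section 1.5.3 is mixed. The myocardial infarction line contains the diagnostic criteria, and the pulmonary vein stenosis line contains the 70% threshold. The tamponade and death lines read as evidence to collect. Both readings of the stroke line are therefore open.

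**Step 3. The plan's own safety figure.** Inputs from protocol 9.7 and SAP 10.1: n = 102, assumed MAE rate 12%, one-sided 95% interval, stated half-width 5%, upper bound below 20%.

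Wald half-width = 1.645 × √(0.12 × 0.88 / 102) = 0.0529, or 5.3 points. The upper bound is 12% + 5.3% = 17.3%. The stated 5% reproduces.

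**Step 4. What a lost event does.** One event is 1/102 = 0.98 percentage points. For x events, the Wald bound is p + 1.645 × √(p(1 − p)/102) with p = x/102. The exact (Clopper-Pearson) bound is the 95th percentile of a Beta(x + 1, 102 − x) distribution.

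| MAEs | Rate | Exact bound | Wald bound |
|---|---|---|---|
| 12 | 11.8% | 18.4% | 17.0% |
| 13 | 12.7% | 19.5% | 18.2% |
| 14 | 13.7% | 20.6% | 19.3% |
| 15 | 14.7% | 21.7% | 20.5% |
| 16 | 15.7% | 22.8% | 21.6% |

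By the exact method, 13 events pass and 14 fail. Losing one event changes the conclusion if the true count is 14, and losing two changes it if the true count is 14 or 15. By Wald, 14 pass and 15 fail, so the corresponding counts are 15 and 16. The documents do not name the method.

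**The case against.** A reader might infer that hemorrhagic and short strokes are simply excluded from the MAE count. The documents do not support that. The definition counts them expressly, and SAP 10.1 points to section 1.5.3 as a whole, not to its documentation sentences. A CEC that follows the definition would count every such event as a stroke. The short deficits also fit the one-line TIA description, so even under a stricter reading they need not vanish. Fatal cases count as Death when the death falls in the window.

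A reader might also infer that one or two events would decide the result at the plan's expected rate. They would not. At 12% of 102, about 12 events, the criterion is met with or without them. The sensitive counts lie above the assumed rate. SAP section 10 also says that safety endpoints are not formally tested.

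Finally, a rejected event would remain visible: Listing 16.2.7.2 shows potential MAEs that the CEC did not accept, and adverse events are summarized for both arms.

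All of this stands, and it limits the size of the problem. It does not remove the conflict, because no text gives the definition precedence, and a listing does not restore an event to the primary safety count.

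**Conclusion.** The two stroke rules in protocol 1.5.3 contradict each other, and nothing in the protocol or SAP settles which one governs adjudication. Loss of events is conditional: it occurs only if the CEC treats the documentation sentence as a qualifying criterion. It would then affect non-fatal hemorrhagic strokes and deficits under 24 h with a new infarct, while treated short deficits without infarct could move from stroke to TIA.

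The likely numerical effect cannot be estimated, because the documents give no stroke rate. At n = 102, one or two lost events would change the below-20% conclusion only at a true count of 14 or 15 (exact) or 15 or 16 (Wald). The conflict should be corrected because it leaves a primary safety component open to two readings. The documents do not show that the safety conclusion is wrong.

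**What to change.** State in protocol 1.5.3 that the definition paragraph governs adjudication. Replace the stroke documentation sentence with documentation of any event that meets the definition, ischemic or hemorrhagic, confirmed by any method the section accepts, including lumbar puncture. Removing only the ischemic and 24-hour wording would not be enough: the remaining list of CT, MRI and angiography would still leave out hemorrhage confirmed by lumbar puncture alone.

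Define TIA as a deficit under 24 h, with no new infarct or hemorrhage on imaging, that does not meet the stroke definition. The last condition is needed because a treated short deficit without infarct would otherwise be both stroke and TIA. Each event then falls into one category.

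The cost is a short protocol change, a matching change to the CEC form, and a recheck of neurological events already adjudicated. The downside for the sponsor is that the MAE rate may be slightly less favourable.

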#### 1.5.4 Secondary Safety Endpoint

The secondary safety endpoint for the study will be the incidence of serious adverse events (SAEs) in the study through the 12 month post procedure visit, in each arm of the study.

#### 1.5.5 Exploratory Endpoints

- Success or failure to achieve a 90% reduction from baseline AF burden with and without Class I and III AADs at 18 months post procedure
- Change in left ventricular ejection fraction
- Atrial remodeling assessed by a decrease in left atrial size

- Health Economics Data
  - Change in number of hospitalizations and total number of days hospitalized for the 12 months (6 months to 18 months post procedure) post procedure period compared to hospitalizations 12 months prior to the procedure
  - Change in rhythm disturbance treatments (e.g. electrical or pharmacological cardioversion, AAD therapy, supraventricular ablative therapy) 12 months (6 months to 18 months post procedure) post procedure period compared to 12 months prior to the procedure

### 1.6 Duration of Investigation

Based on an enrollment of 153 randomized persistent AF subjects, it is anticipated that all subjects will be enrolled within 36 months after study initiation. The study will end when the last enrolled subject completes the 12 month post-procedure follow-up visit. Therefore, study duration is anticipated to be approximately 48 months.

## 2.0 DEVICE DESCRIPTION

### 2.1 EPi-Sense®-AF Guided Coagulation System with VisiTrax® Overview

The fourth generation coagulation device, EPi-Sense Guided Coagulation System with VisiTrax®, has been cleared for the endoscopic coagulation of cardiac tissue (510k K120857, K142084). The subject device for this study will be labeled EPi-Sense®-AF Guided Coagulation System with VisiTrax® *For Investigational Use Only*.

The device consists of a flexible radiofrequency coil electrode assembly that can be applied consistently to the epicardial surface of cardiac tissue by vacuum (designed to eliminate gaps along the lesion), a perfusion component designed to keep the tissue surface hydrated and the device surfaces not contacting cardiac tissue cool throughout the coagulation process, and sensing electrodes between select coil electrode windings to transmit cardiac electrograms to an external EP Recording System and transmit pacing pulses from an external stimulator; the complete Coagulation System also includes a customized RF generator that transmits energy to the device, and accessory cables to connect the coagulation device to the RF generator and route sensing electrode signals to an external EP Recording System. The Cannula Accessory is also provided to facilitate access for operative and diagnostic instrumentation including the EPi-Sense-AF Guided Coagulation device with VisiTrax, and enable endoscopic visualization throughout the lesion creation procedure.

The EPi-Sense-AF Guided Coagulation System with VisiTrax has been designed to provide the following benefits:

- Consistent contact with epicardial cardiac tissue regardless of cardiac anatomy
- Precise lesion creation without damage to surrounding tissue
- Continuous and complete lesions
- Visible lesions to interconnect into a pattern
- Device maneuverability to perform the coagulation of cardiac tissue under direct endoscopic visualization without chest incisions or lung deflation
- Use of temporary cardiac signal sensing to confirm device location.

The EPi-Sense-AF Guided Coagulation System with VisiTrax is able to coagulate cardiac tissue from the epicardial surface. The ability to coagulate tissue epicardially allows the procedure to be performed on a beating heart. The ability to access the posterior epicardium allows the procedure to be performed endoscopically without chest incisions, lung deflation, or dissections of the pericardial reflections (attachments between the pericardium and atrium).

The Operator's Manual for the RF Generator and the Instructions for Use for the EPi-Sense-AF Guided Coagulation System with VisiTrax and the Cannula Accessory must be reviewed prior to system use.

### 3.0 BACKGROUND

#### 3.1 Atrial Fibrillation

AF is characterized by very fast, irregular beating of the heart's upper chambers (the atria). It occurs when normal sinus rhythm is disrupted by errant irregular electrical signals in the atria. These erratic electrical propagation patterns disrupt the regular pumping action of the atria, preventing complete filling of the ventricles, and causing irregular beating of the ventricles. These spasms often lead to regions of static blood flow in the atria and consequently, blood clot formation, stroke and even death. It is estimated that AF is responsible for 15% - 25% of all strokes. Symptoms of AF typically include a rapid and irregular heartbeat, palpitations, dyspnea, discomfort, dizziness and fatigue.

Atrial fibrillation (AF) is a common heart arrhythmia that carries a significant mortality and morbidity risk, and is associated with three primary clinical sequelae: loss of atrial transport, loss of regular cardiac chamber synchronization, rhythm & rate response, and thromboembolism. Up to a third of all patients with persistent AF will experience at least one embolic episode during the course of their atrial fibrillation. Lone AF (e.g. no structural heart disease) with no left atrial enlargement may be categorized as a benign disease since it is not associated with an increase in mortality or complications than that of the general population. However, AF patients, especially those with enlarged atria or structural heart disease, are at an increased risk of congestive heart failure, thromboembolic events, and mortality.i In fact, permanent AF (longstanding persistent AF after the decision not to treat) is associated with 8.2% annual all-cause mortality, 5.1% annual thromboembolic event rate, 2.7% annual major bleeding rate, and 16.6% annual heart failure rate.ii

The underlying theory surrounding the source of irregular conduction pathways in patients with atrial fibrillation involves ectopic electrical activity or micro-reentrant circuits that can originate from specific locations in the heart such as the pulmonary vein orifice in patients with lone AF (focal), or more commonly associated with the reentry of conduction circuits throughout the atria in patients with structural remodeling (wavelet AF).

Only 12% of patients have Lone AF, leaving the remaining 88% with some form of structural heart disease.iii This structural heart disease commonly includes hypertension, coronary artery and valvular heart disease. Left untreated, AF can lead to ventricular dysfunction, atrial dysfunction, left atrial enlargement thus perpetuating the structural remodeling that causes and worsens atrial fibrillation and heart failure.iv

The relationship between progressive structural remodeling and atrial fibrillation explains why 88% of AF patients are persistent or permanent leaving only 12% as paroxysmal.v Furthermore, 76% of AF patients either have enlarged atria with diameter greater than 4.5 cm or an increase in left ventricular thickness.vi Atrial enlargement, as well as structural remodeling, determines the incidence of atrial fibrillation and whether AF patients observe complications throughout their lifetime.

iOsranek M. Left atrial volume predicts cardiovascular events in patients originally diagnosed with lone atrial fibrillation: three-decade follow-up. European Heart Journal (2005) 26, 2556–2561.

ii Nieuwlaat R, et al. Prognosis, disease progression, and treatment of atrial fibrillation during 1 year: follow-up of the Euro Heart Survey on atrial fibrillation. Eur Heart J. 2008;29:1181-1189.

iii Fuster and Rydén et al. ACC/AHA/ESC Practice Guidelines. JACC Vol. 38, No. 4, October, 2001.

iv Ommen SR, et al. Usefulness of serial echocardiographic parameters for predicting the subsequent Thisoccurrence of atrial fibrillation. Am J Card. Vol 87. June 1, 2001.

v Atrial Fibrillation Investigators. Risk factors for stroke and efficacy of antithrombotic therapy in atrial fibrillation. Arch Intern Med 1994;154:1449-1457.

vi Pritchett A, et al. Left Atrial Volume as an Index of Left Atrial Size: A Population-Based Study. J Am Coll Cardiol 2003;41:1036–43.

Patients newly diagnosed with AF are medically managed with multiple courses of antiarrhythmic drugs (AAD), and anticoagulants to lessen the risk of thromboembolic accidents. Within 5 years, most patients will become refractory to AADs, and will require additional intervention. Often AADs will have the effect of “dumbing down” the heart’s natural pacemaker, necessitating the need for permanent rate control. Although the risk of thromboembolism is reduced in the presence of anticoagulation, it is still substantially higher than that observed in the general population. In addition, bleeding complications from anticoagulation regimens occur at a cumulative rate of 1% per year.

### 3.2 Atrial Fibrillation Classification

The HRS/EHRA/ECAS (2012) Guidelines have classified AF into 3 groups.vii

- Paroxysmal AF is defined as recurrent AF (>2 episodes) that terminates spontaneously within seven days.
- Persistent AF is defined as AF which is sustained beyond 7 days. Episodes of AF which are terminated by electrical or pharmacologic cardioversion after  $\geq$  48 hours of AF, but prior to 7 days, should also be classified as persistent AF episodes.
- Longstanding persistent AF is defined as continuous AF greater than one-year duration.

The term permanent AF is not appropriate in the context of patients undergoing ablation of AF as it refers to a group of patients where a decision has been made not to pursue restoration of sinus rhythm by any means, including catheter or surgical ablation.

### 3.3 Treatment of Atrial Fibrillation

As described in 3.1, AF is typically first treated with drug therapy, with an approximately equal split between rate and rhythm control drugs as first line of treatment. Recent large scale studies have failed to show superiority of one treatment approach - rate or rhythm control - over another. Regardless of rate or rhythm control, continuous anticoagulation therapy is crucial in AF patients for stroke prevention. The AFFIRM study concluded that the benefit of restoring sinus rhythm in the rhythm control group was reversed by the toxicity of the antiarrhythmic drugs and hypothesized that if a treatment was available to restore sinus rhythm without the toxicity of antiarrhythmic drugs, survival may be improved.

Drug therapy failure may be due to either a lack of medication efficacy and/or a patient’s inability to tolerate medications known to have serious and bothersome side effects, including those resulting from interactions with other drugs. According to its package insert, Cardarone® (amiodarone), the most widely-prescribed anti-arrhythmic medication (not approved for the treatment of AF), is discontinued in 7-18% of patients due to intolerable side effects.

Surgical treatment of AF is usually considered when a patient is already scheduled for a concomitant cardiac procedure requiring access to the thoracic cavity. When performed concomitantly, the surgical treatment of AF is often performed using cardiopulmonary bypass on an open and arrested heart. The surgeon is unable to observe atrial function and cannot confirm treatment success intraoperatively because the atria must be beating in order to place a pacing electrode and confirm conduction block.

The Maze procedures (and its derivatives, Maze III, etc.), are considered the comparative standard for the effective treatment of AF. The Maze III procedure requires stopping the heart and then surgically cutting and re-sewing the atria to create a complex pattern of lesions throughout the atria that are intended to block macro-reentry circuits within the atria. In the intervening years, the Maze III procedure has been modified, but it remains the standard for

vii 2012 HRS/EHRA/ECAS expert consensus statement on catheter and surgical ablation of atrial fibrillation: recommendations for patient selection, procedural techniques, patient management, and follow-up, definitions, endpoints, and research trial design. J Interv Card Electrophysiol. 2012;33(2):171-257.

treatment of atrial fibrillation. However, associated procedural mortality (2 to 10%) and morbidity including permanent pacemaker requirements (~15% of patients) have hindered the adoption of "cut and sew" procedure.

There have been many attempts to move away from the complexity and risk of the cut and sew Maze III procedure. Most of the effort has focused on procedures to isolate errant conduction signals that are suspected to originate from the pulmonary veins either by segmental ostial ablation or by the creation of a box lesion around the pulmonary veins. Electrically isolating the pulmonary veins may be effective for focal AF patients who have paroxysmal AF with no structural heart disease. However, more complex types of AF require a more comprehensive lesion pattern to block all reentrant circuits, and therefore sole isolation of the pulmonary veins is not an effective treatment.

To date, a percutaneous catheter-based or minimally invasive surgical procedure that can effectively and safely treat persistent or longstanding persistent Atrial Fibrillation (AF) is unavailable.

The ideal treatment for AF would mitigate the detrimental sequelae of AF; that is, the procedure would restore normal sinus rhythm and cardiac hemodynamics, prevent continued remodeling and enlargement of the atria, and reduce the risk of thromboembolism. The ideal procedure would provide a means for assessing completeness of the lesion patterns. Continuous and complete lesions created throughout the atria and electrically silencing the posterior left atrium as well as isolating the pulmonary veins are most likely to prevent propagation of electrical signals capable of inducing and/or maintaining AF, and prevent development of new reentrant circuits or atrial enlargement. The ideal procedure would also be performed utilizing minimally invasive, closed chest techniques.

AtriCure has developed a cardiac tissue coagulation system that may provide improved performance over current treatment options. Atricure's technology is based on a low profile, flexible radiofrequency (RF) coagulation device that provides consistent contact with the tissue through the use of vacuum. The technology ensures reliable contact, conformation to any tissue region of the heart, as well as localized-directional treatment to make conventional cardiac tissue coagulation more predictable. The system also incorporates a perfusion lumen coupled to the vacuum source that 1) hydrates tissue that is in contact with the device electrode, and 2) cools the non-tissue contacting surfaces of the device. The vacuum perfused device design controls energy delivery, minimizes the risk of over-heating tissue that is being coagulated and thus, the risk of charring and tissue vaporization, and also prevents damage to non-targeted, adjacent tissues and anatomical structures.

The inclusion of sensing electrodes to the coagulation device has provided additional input to the operator as to the type of tissue targeted for ablation and evaluation of the extent of ablation. Electrograms, recorded from tissue against which the coagulation electrode contacts, augment the direct endoscopic visualization of electrode position by determining definitively that the sensing electrodes, thus the coagulation electrode, contact target atrial tissue. The sensing electrodes provide input throughout energy delivery on the extent and completeness of cardiac coagulation by delineating electrically viable tissue from non-viable tissue which coincides with a substantial reduction in cardiac electrogram amplitude. In addition, the sensing electrodes allow transmission of pacing stimuli to tissue for evaluating the isolation of the posterior left atrium and pulmonary vein isolation at locations accessible from a transdiaphragmatic or sub-xiphoid pericardial window.

AtriCure has taken the coagulation of cardiac tissue one step further with the Guided Coagulation System that allows the procedure to be performed without the need for chest incisions. The use of a cannula facilitates access and provides visibility to the posterior surface of the heart allowing the creation of lesions on the epicardium of the atria under direct visualization.

The one limitation, which ends up being a substantial benefit, of the closed chest, transdiaphragmatic or sub-xiphoid access is the inability to dissect the pericardial reflections (attachments between the atria and pericardium). This reduces the perforation risks since those dissections are adjacent to thin, fragile tissue but hinders the ability to create lesions completely around the pulmonary veins. The reflections are short, and are located above the right and left superior pulmonary veins and below the right inferior pulmonary vein. To address this limitation, AtriCure has proposed treatment for persistent AF that incorporates endocardial catheter ablation to complete pulmonary vein isolation by ablating known breakthrough locations in the epicardial linear lesions at the pericardial reflections, and ablate the cavotricuspid isthmus to prevent typical AFL. This multidisciplinary approach combines epicardial and endocardial ablation procedures into a truly minimally invasive approach that does not require chest incisions or lung deflation. AtriCure is proposing this randomized pivotal study to evaluate the safety and efficacy of the EPi-Sense-AF Guided Coagulation System with VisiTrax for the treatment of symptomatic persistent AF. The premise of this Convergent Procedure stems from the complementary nature of both approaches.

